8.2 Advancement through the HIV Prevention or Care Continuum

Advancement through the HIV Prevention or Care Continuum will be assessed at all time points throughout the study, and will be operationalized dichotomously (i.e., yes/no achievement of one of the steps on either the HIV Prevention or Care Continuum; e.g., viral suppression), and

as a counted variable (e.g., consecutive DBS results indicating successful PrEP adherence). Power calculations related to advancement through either continuum will assume a 30% probability of achievement of at least one of the steps on either the HIV Prevention or Care Continuum (equivalent to ~1:2 odds of advancement). Methamphetamine use outcomes will be assessed repeatedly (i.e., at all time points) and will be operationalized dichotomously (e.g., methamphetamine-metabolite-free urine sample), as a counted variable (i.e., number of methamphetamine-metabolite-free urine samples provided), and as a continuous variable (i.e., Treatment Effectiveness Score [total number of methamphetamine-metabolite-free sample divided by total samples possible]). Power calculations related to methamphetamine use outcomes assume an 80% probability of methamphetamine use during the pre-intervention period for participants in the DD arm (equivalent to 4:1 odds of use).

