2.0 INTRODUCTION

2.1 Rationale

Methamphetamine use among MSM is associated with increased rates of HIV prevalence and transmission, as well as substandard advancement along the HIV Prevention and Care Continua. Methamphetamine use among MSM is deeply integrated into socio-sexual networks including the use of smartphone apps and websites to find sexual partners. Given the growth of mobile health technology, it is no longer necessary or reasonable to limit methamphetamine treatment options to physical sites, clustered in urban areas, and administered using generic, non-tailored content. The project builds upon the established efficacy of our manualized methamphetamine-use treatment intervention, “*Getting Off: A Behavioral Treatment Intervention for Gay and Bisexual Male Methamphetamine Users*,” and the highly promising findings from the successful Stage I proof-of-concept study, to complete translation of *Getting Off* into a cross-platform (iOS and Android) app and assess the app’s efficacy *and* non-inferiority in a scientifically rigorous randomized trial. The *Getting Off* app, like the group-based intervention before it, will use the principles of Cognitive Behavioral Theory and Stages of Change to help MSM reduce or eliminate methamphetamine use and HIV sexual risk behaviors, and increase advancement along the HIV Prevention or Care Continuum (including uptake of HIV testing, pre-, and post-exposure prophylaxis [PEP/PrEP] and PrEP adherence and persistence for those who are HIV negative; ART uptake and adherence for those who are HIV positive).

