6.6.2 Behavioral Assessments

6.6.2.1 DSM-5 Methamphetamine Use Disorder contains the DSM-5 diagnostic items necessary to make a determination of mild, moderate, or severe methamphetamine use disorder. This information will determine the app's utility for consumers at various levels of methamphetamine use. DSM-5 diagnostic criteria for other substance use disorders will also be collected. Administered at baseline only.

6.6.2.2 University of Rhode Island Change Assessment (URICA) is a brief, self-administered inventory used to assess the participant's current position regarding readiness for change (e.g., precontemplation, contemplation, action). Administered at all time points.

6.6.2.3 Admission/Follow-up Form collects demographic information, housing status, food security, educational attainment, alcohol and other drug use history, family and social history, legal status, HIV status, location on the HIV Prevention or Care Continuum, experiences with stigma and/or discrimination, and general and mental health status. The full form will be administered at baseline, an abbreviated version at all follow-up time points.

6.6.2.4 Substance Use Frequency is a brief assessment, developed by [name] (Principal Investigator) that assesses substance use, injection drug use, and injection protocols in the past 30 days. Administered at all time points.

6.6.2.5 Behavioral Questionnaire – Amphetamine (BQA)-Abbreviated Version gathers information on HIV-related drug and sexual risk behaviors, assesses self-efficacy for sexual behavior change, and collects detailed information on discrete sexual behaviors (with primary or non-primary partners and whether or not the behavior occurred under the influence of methamphetamine and/or other substances), as well as episodic data about participants' most recent sexual encounters. Administered at baseline, and an abbreviated version is administered at all follow-up time points.

6.6.2.6 PrEP Uptake and Adherence is a brief assessment, developed by [name] (Principal Investigator), that gathers information of PrEP readiness, initiation and adherence to access advancement along the HIV Prevention Continuum. Administered at all time points.

6.6.2.7 ART/HIV Care is a brief assessment, developed by [name] (Principal Investigator), that gathers information of HIV care and ART medication adherence to access advancement along the HIV Care Continuum. Administered at all time points.

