6.6.3. Biomarker Assessments

6.6.3.1 HIV-antibody Test. HIV-negative and status unknown participants will receive a fingerstick DBS test at 3-month intervals, as recommended by the CDC for high-risk individuals. Participants who show documentation of HIV-positive serostatus are not given a HIV-antibody test. If the test is reactive, then the participant will be presumed positive for HIV antibodies and referred for additional evaluation and treatment. If the DBS sample is rejected by the lab or if the quantity of blood is insufficient, participants will be asked to come to the study site to have the test performed via fingerstick blood test using the INSTI HIV 1/HIV 2 antibody test, or to provide a copy of recent results (within 3 months) from their medical provider. Conducted at baseline and at the 3-, 6-, and 9-month follow-up time points (if previously tested HIV-negative or status is unknown).

6.6.3.2 STI Testing. Participants will be tested for urinary N. gonorrhoea and Chlamydia, pharyngeal and rectal swabs will be taken for N. gonorrhoea and Chlamydia, and syphilis will be tested by fingerstick DBS. Positive STI results will be reported per state guidelines and will be immediately referred to care. If the DBS sample is rejected by the lab or if the quantity of blood is insufficient, participants will be asked to come to the study site to have the test performed via intravenous blood draw or to provide a copy of recent results (within 3 months) from their medical provider. Conducted at baseline and at the 3-, 6-, and 9-month follow-up time points.

6.6.3.3 Virologic Control for HIV-positive Participants. As indicated by an undetectable HIV-1 level via intravenous blood draw, which has a threshold for undetectability = <30 copies/mL will be performed by Foundation Laboratory. Viral load testing through Foundation Laboratory may be bypassed if participants can provide recent (within 3 months) lab results from their medical provider. Conducted at baseline and at the 3-, 6-, and 9-month follow-up time points.

6.6.3.4 Dried Blood Spot (DBS) for HIV-negative Participants who Report PrEP Uptake. A blood sample will be collected and a DBS analysis for intra-erythrocytic TFV-DP will be performed by Molecular Testing Labs. Conducted at baseline and at the 3-, 6-, and 9-month follow-up time points.

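### Section 8.2 does not say whether 'advancement' must be a step new since baseline, or whether the study's own HIV tests count as a step

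*Combined protocol and SAP*

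**What the plan says.** Section 8.2 scores the outcome at all time points and gives the dichotomous rule as "i.e., yes/no achievement of one of the steps on either the HIV Prevention or Care Continuum; e.g., viral suppression". The power calculations "assume a 30% probability of achievement of at least one of the steps", with the gloss "equivalent to ~1:2 odds of advancement".

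Table 2 lists HIV Test, PrEP Uptake and an advance along either continuum as dichotomous versions, without a scoring rule. Its footnote a names the steps: HIV testing and PrEP/PEP uptake on the prevention side; linkage, ART adherence and virological suppression on the care side. Section 2.1 spells out what advancement includes, among other things "PrEP adherence and persistence for those who are HIV negative; ART uptake and adherence for those who are HIV positive".

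On data, the Admission/Follow-up Form (6.6.2.3) records "HIV status, location on the HIV Prevention or Care Continuum", in full at baseline and abbreviated later. Self-reported PrEP and ART/HIV care are taken at every visit (6.6.2.6, 6.6.2.7). Under 6.6.3.1, "HIV-negative and status unknown participants will receive a fingerstick DBS test at 3-month intervals", and the schedule is "Conducted at baseline and at the 3-, 6-, and 9-month follow-up time points (if previously tested HIV-negative or status is unknown"). Viral load and the "Dried Blood Spot (DBS) for HIV-negative Participants who Report PrEP Uptake" follow the same calendar. None of these tests is scheduled at month 1 or 2.

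**The concern.** The outcome is named for change, but its rule describes having a step. Two questions are left open.

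- **Steps held at entry.** Eligibility (5.1, 5.2) does not screen on PrEP, ART, linkage or suppression, and the baseline PrEP blood spot and viral load show that such men are expected. Under the literal rule they score *yes* at every visit with no change.
- **Study-supplied tests.** HIV testing is a step, and the study itself tests HIV-negative and status-unknown men. Section 6.5 pays for returned kits. Completing a study procedure could then score as advancement.

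Advancement is an outcome in all three specific aims. Two analysts could follow 8.2, obtain different *yes* rates from the same data, and choose between them after seeing results. Men fixed at *yes* in both arms carry no information about the app, and a *yes* need not mean that anyone advanced.

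**Working it through.** **1. The plan's own figure.** Inputs: 30% reference rate (8.2); 150 per arm and OR 1.97 (9.1); two-sided 0.05 and 80% power (8.3). The odds are 0.30/0.70 × 1.97 = 0.844, so the comparison rate is 0.844/1.844 = 45.8%. Wald test on the log odds ratio: ln 1.97 = 0.678; SE = √[1/(150×0.30×0.70) + 1/(150×0.458×0.542)] = 0.242; 0.678/0.242 − 1.96 = 0.84, so power is 0.80. The stated figure reproduces. The pooled two-proportion formula used below gives 0.81.

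**2. Which visits each question reaches.**

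| | Month 1 (DD not yet using the app) | Aim 1b pairs (enrollment, months 1 and 2) | Months 3, 6, 9 |
|---|---|---|---|
| Step held at entry, self-reported (PrEP, ART, linkage) | yes | yes | yes |
| Suppression held at entry | not measured | measured at enrollment only | yes |
| Study HIV test | only if the baseline test counts | only if the baseline test counts | yes |

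**3. Illustration of the dilution at month 1.** Let *s* be the share fixed at *yes* in both arms. The documents do not give *s*, so it is assumed. The other men respond at 30% vs 45.8%. Power = Φ{[|p₂−p₁|√n − 1.96√(2p̄(1−p̄))] / √[p₁(1−p₁)+p₂(1−p₂)]}.

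- Follow-up only, unadjusted: p = s + (1−s) × rate, n = 150.
- Change from baseline: men already at *yes* show no change, so the rate of change is (1−s) × rate, n = 150. This is the same quantity as scoring new steps only.
- Baseline status as a covariate: the information comes from the 150(1−s) men per arm not already at *yes*, at 30% vs 45.8%.

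| s | Follow-up only | Change from baseline / new step | Baseline-adjusted |
|---|---|---|---|
| 0 | 30.0 vs 45.8%: 0.81 | 30.0 vs 45.8%: 0.81 | n=150: 0.81 |
| 0.20 | 44.0 vs 56.6%: 0.59 | 24.0 vs 36.6%: 0.66 | n=120: 0.71 |
| 0.50 | 65.0 vs 72.9%: 0.31 | 15.0 vs 22.9%: 0.41 | n=75: 0.51 |

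Simulating linear models under the literal rule agrees: about 65% and 42% for change from baseline, and about 71% and 51% with baseline status as a covariate. The further gain in power comes from the covariate. Rescoring alone does no better than a change analysis of the literal score.

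**4. Study tests from month 3.** If completed tests count, the *yes* rate at months 3, 6 and 9 is at least (share HIV-negative or unknown) × (completion). Neither is given for the trial. For shares of 33%, 50% and 67%, the floor is 33%, 50% and 67% at full completion, or 23%, 35% and 47% at 70% completion. The 33% would match the pilot (67% HIV-positive, N=15).

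**5. If the expected rate under a new-step rule is not 30%.** The same Wald calculation gives a minimum detectable OR of 2.11 at 20% and 2.56 at 10% (both rates assumed).

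**The case against.** The strongest reply is that change was plainly meant. The word advancement, the phrase "equivalent to ~1:2 odds of advancement", and the Table 2 entries on uptake and advancing are all change words. That is a fair reading, but Section 2.1 puts persistence, which is keeping a step, under the same heading. A change reading also leaves open whether study tests count.

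Second, the plan does not propose an unadjusted follow-up-only test. It uses mixed-effects models on repeated measures (8.1, 8.3), with power based on two time points such as baseline and app completion. Table 2 lists HIV status and linked/unlinked as potential controls, and 6.4 balances randomization on serostatus. This stands in part: a reader might infer that the trial's power falls to 59% or 31%, and the documents do not support that. However, those controls enter only through the significance screen in 8.1, and nothing commits the analysis to adjusting this outcome for baseline continuum location.

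Third, Table 2 puts HIV Test in the Admission/Follow-up Form row and study tests in a separate biomarker row, whose dichotomous entry is incident STI or HIV. This weakens the inference that study tests count. It does not settle it, because the biomarker row's target also includes continuum outcomes.

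The illustration has its own limit. The literal rule fixes holders of any step at *yes*, whereas a new-step rule fixes only men at the top step at *no*. One value of *s* treats these as the same group.

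**Conclusion.** The concern holds as an undefined scoring rule that can label men as advanced when nothing changed. It should be settled before analysis. Confidence is moderate, because the intended meaning may well be change.

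Four stronger inferences are not supported:

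- That the randomized comparison is biased. Held steps should be balanced by randomization, so the effect is dilution.
- That study tests contaminate the month-1 contrast or the Aim 1b pairs. None is scheduled at month 1 or 2, so this requires the baseline test to count. They bear on the month 3 to 9 longitudinal results.
- That Aim 1c is biased. This would need visits at month 3 or later and a historical group tested on a different schedule, and the documents describe neither.
- That OR 1.97 is wrong. It reproduces; what is unclear is which definition the 30% describes.

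The size rests on the assumed *s*. At 20% or 50%, the gap between the unadjusted follow-up-only test and the baseline-adjusted one is about 12 or 20 percentage points of power (71 − 59; 51 − 31).

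**What to change.** In Section 8.2 and Table 2:

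1. Name baseline continuum location as a prespecified covariate for this outcome in Aim 1a, rather than leaving it to the screen in 8.1. This is where the power gain lies.
2. Do not count completion of a study-supplied HIV, viral load or blood-spot test as a step. Results such as suppression may count. State the look-back period for an outside HIV test.
3. Score Aim 1a advancement as a step not held at baseline, and report persistence as a separate outcome. For Aim 1b, compare steps held at the pre-app and post-app visits, because a new-step score is *no* by construction for every ID participant at enrollment. The main gain here is that *yes* means advancement.
4. State that the 30% refers to this definition, and restate the detectable effect only if the expected rate differs.

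The cost is mostly wording, since baseline location is already collected. One follow-up item may be needed to separate outside tests from study tests, unless the abbreviated form already has it. On the downside, men at the top step cannot advance and become fixed at *no*, and outside HIV tests may be few while the study tests every three months.

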6.3 Enrollment Procedures

After the Informed Consent Form for the study has been read, any questions have been answered, the informed consent quiz has been passed, and the participant has electronically signed the consent form, a Research Coordinator or RA will deliver the baseline assessment, which takes approximately 60-90 minutes. To maximize accurate disclosure of high-risk and sensitive behaviors, data is collected via an audio computer-assisted self-interview (ACASI). Studies have demonstrated that disclosure rates of perceived stigmatized behaviors are increased through ACASI assessments. After the ACASI is completed, participants will be instructed to download the *Getting Off* app on to their smartphone. Once access to the app is granted (determined by randomization), participants will have 30-days to complete the 24 sessions.

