6.5 Incentive Schedule

Incentives are comprised of 1) incentives for baseline assessment (\$40 gift card); 2) incentives for completing follow-up assessments [\$50 gift card for completing the 1-month follow-up assessment, the 2-month follow-up assessment (DD arm only), the 3-month follow-up assessment, the 6-month follow-up assessment, and the 9-month follow-up assessment]; 3) incentives for self-administering and returning the at-home HIV/STI test kits within 45 days of receipt [\$50 gift card for returning after the 3-month assessment, after the 6-month assessment, and after the 9-month assessment] and 4) a \$2 gift card when an active participant brings a potential participant to the site to screen for eligibility, and an additional \$18 gift card if the potential participant is eligible and enrolls (maximum of three eligible and enrolled participants per active participant). Participants randomized into the ID arm can thus earn a maximum of \$450 in gift cards. Participants randomized into the DD arm can earn a maximum of \$500 in gift cards.

All participants may earn up to \$50 in gift cards each time they provide all requested biological marker samples or test results at the follow-ups, if conducted at-home and returned within 45 days of receiving the kit. HIV-positive participants may earn a \$20 gift card for returning a complete at-home test kit for Chlamydia, N. gonorrhoea and Syphilis. If the DBS sample is insufficient for processing the Syphilis test, participants will be asked to provide results of a recent (within 3 months) Syphilis test from their medical provider, or to come to the study site for an in-person blood draw. HIV-positive participants may earn the additional \$30 gift card (totaling \$50 in gift cards) for providing recent (within 3 months) HIV viral load test results from their medical provider, or by coming to the study site for a blood draw. HIV-negative participants may earn the full \$50 gift card for returning a complete at-home test kit for Chlamydia, N. gonorrhoea, Syphilis and HIV. Including, an additional DBS card for PrEP (TDF/FTC or TAF/FTC), if

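### Section 8.2 and Table 2 rely on urine drug tests that sections 6.6.3 and 6.5 do not list; as scheduled, the only continuous methamphetamine outcome cannot be computed and month 1 has self-report only. Separately, the f2 in 9.1 disagrees with Table 2.

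*Combined protocol and SAP*

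**What the plan says.** Section 8.2, although headed for the continuum outcome, also holds the methamphetamine definitions. It says: "Methamphetamine use outcomes will be assessed repeatedly (i.e., at all time points) and will be operationalized dichotomously (e.g., methamphetamine-metabolite-free urine sample"). The count form is given "as a counted variable (i.e., number of methamphetamine-metabolite-free urine samples provided"), and the continuous form is the "Treatment Effectiveness Score [total number of methamphetamine-metabolite-free sample divided by total samples possible"]. The dichotomous form cites urine as an example; the other two are definitions. Table 2 has a biomarker row that includes UA, with methamphetamine use among its targets and the Treatment Effectiveness Score as its continuous variable. A separate Substance Use Frequency row holds the self-report forms (use/non-use, days of use), with the continuous form marked N/A.

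Section 6.6.3 lists four biomarkers: HIV antibody, STI, viral load, and dried blood spot for PrEP. The only urine in it is for infection: "Participants will be tested for urinary N. gonorrhoea and Chlamydia". The timing is "Conducted at baseline and at the 3-, 6-, and 9-month follow-up time points". Section 6.5 describes the kit for HIV-negative participants as "returning a complete at-home test kit for Chlamydia, N. gonorrhoea, Syphilis and HIV", plus a PrEP card where relevant; no kit it describes contains a drug test.

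On self-report, 6.3 says: "To maximize accurate disclosure of high-risk and sensitive behaviors, data is collected via an audio computer-assisted self-interview (ACASI"). Section 6.6.2.4 gives the Substance Use Frequency form at every visit. Section 4.0 allows virtual follow-ups, and 9.1 describes the trial as non-blinded.

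For Aim 1a, 9.1 states f2 = 0.05 for both methamphetamine and sexual risk. Table 2 states 0.03 for both.

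**The concern.** The sections that define the methamphetamine outcome and the sections that schedule its measurement do not agree. If the schedule is followed, one of the three planned forms has no data, the count cannot be formed as 8.2 words it, and the cross-modality comparison foreseen in 8.1 has no biomarker for methamphetamine.

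Month 1 is where this matters most. The delayed arm receives the app after 30 days, so month 1 is the only follow-up at which one randomised arm has had the app and the other has not. Months 3 to 9 are still randomised, but they compare immediate with delayed access. A reader cannot tell whether the month-1 methamphetamine result is meant to be biologically confirmed or self-reported by participants who know their arm. If this stays open until the data are in, the choice between urine and self-report could follow the results.

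The two f2 values for Aim 1a are a separate problem: the plan gives two different detectable effects for the same comparison.

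**Working it through.** **1. Scheduled visits and tests** (sections 3.1, 6.6.1, 6.6.3)

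- Immediate arm: baseline and months 1, 3, 6, 9, which is 5 visits.
- Delayed arm: baseline and months 1, 2, 3, 6, 9, which is 6 visits.
- Biomarker visits in 6.6.3: baseline and months 3, 6, 9.
- Urine drug tests listed in 6.6.3: 0 of 5 and 0 of 6.
- Any biomarker at month 1: none, in either arm.

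The score is clean samples divided by samples possible. On this schedule it is 0/0. If the STI urine were also assayed for drugs (an assumption), there would be 4 samples per participant, 3 of them after baseline, and still none at month 1.

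**2. What remains measurable.** Self-reported use/non-use and days of use are scheduled at every visit, and Table 2 attaches OR 0.48 and IRR 0.85 to them for Aim 1a. The dichotomous and count analyses can therefore be done from self-report.

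**3. Aim 1a odds ratios, reproduced first.** Inputs: 150 per arm, two-sided 0.05, and control rates from 8.2 and 8.3; for methamphetamine the plan's calculations "assume an 80% probability of methamphetamine use during the pre-intervention period for participants in the DD arm". Formulas:

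- p2 = OR·odds1 / (1 + OR·odds1)
- SE = √{[p1(1−p1) + p2(1−p2)]/150}
- power = Φ(|p1−p2|/SE − 1.960)

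Results:

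- Methamphetamine: p1 = 0.80, OR 0.48; p2 = 1.92/2.92 = 0.6575; SE = 0.0507; Φ(0.851) = 80.3%.
- Sexual risk: p1 = 0.65, OR 0.52; p2 = 0.4913; SE = 0.0564; Φ(0.853) = 80.3%.
- Continuum: p1 = 0.30, OR 1.97; p2 = 0.4578; SE = 0.0553; Φ(0.895) = 81.5%.

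With a pooled null variance these become 79.6%, 79.6% and 80.7%. The stated odds ratios are therefore those of a one-visit comparison of 150 with 150, all observed.

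**4. Aim 1a f2.** Noncentral F test with one tested term and one covariate (the single covariate is stated in 8.3), noncentrality λ = f2·N, alpha 0.05, power 80%. As a rough check, f2 ≈ (1.960 + 0.842)²/N = 7.85/N.

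- N = 300: 7.85/300 = 0.0262; exact 0.026. This rounds to Table 2's 0.03.
- N = 150: exact 0.053.
- f2 = 0.05: 7.85/0.05 = 157; exact about 160 participants.
- Power of N = 300 for f2 = 0.05: 97%.

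Table 2's 0.03 fits the stated sample; 0.05 in 9.1 does not.

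**5. f2 entries with no continuous form.** In Table 2 the Substance Use Frequency row and the continuum row both mark the continuous form N/A, yet both carry f2 values.

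**The case against.** The strongest reply is that urine testing is plainly intended: 8.2 and Table 2 both rely on it, and 6.6.3 does not claim to be exhaustive. That is fair. The documents show a conflict; they do not show that no urine drug tests are done. UA is also absent from the glossary, so reading it as a drug test is an inference, though the row's methamphetamine target and the score support it. What stands is that neither the visits nor the collection route at virtual follow-ups is stated.

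A reader might infer more than the documents support:

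- **That the methamphetamine outcome is lost.** It is not; the self-report forms remain, and ACASI is the plan's measure against under-disclosure.
- **That clean samples and days of use contradict each other because benefit runs in opposite directions.** They come from different instruments, and 8.1 deliberately plans more than one operationalisation. What is missing is which count is primary.
- **That the urine gap causes the f2 discrepancy.** It does not. The 0.05 against 0.03 mismatch also affects sexual risk, which has a self-report scale, and the continuum row carries an f2 without a continuous form.
- **That month 1 is wholly unidentified as the contrast.** Section 8.2 sets rates for the delayed arm before it gets the app, and 8.3 bases power on two time points such as baseline and app completion. Both point to month 1; 9.1 simply does not say so.
- **That naming month 1 costs no power.** The match in step 3 assumes all 300 are observed. It does not compare a single visit with the planned repeated-measures model.
- **That the self-report bias can be sized.** With no true effect and 80% use in both arms, if 5 more of every 100 users in the immediate arm than in the delayed arm deny use, 11 to 13% of trials would be significant; with 10 more, 29 to 37% (0 to 20% denial common to both arms). Those denial rates are assumptions. They illustrate sensitivity and do not estimate this trial's bias.

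**Conclusion.** The inconsistency is real and should be fixed. On the written schedule there are no urine drug tests at any visit, so the Treatment Effectiveness Score and 8.2's count cannot be computed, and the month-1 methamphetamine comparison is self-reported. This holds only if 6.6.3 is followed as it stands; if urine tests are in fact done, the defect is an unlisted procedure with unstated visits.

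The f2 error is separate and firm under the plan's own alpha, power and single covariate: 0.026 at N = 300, against 0.05 in 9.1 and 0.03 in Table 2. The Aim 1a odds ratios are sound and need no change.

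**What to change.** Before outcome data are analysed:

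1. Reconcile 6.6.3, 8.2 and Table 2.
   - If urine drug tests are done, list them in 6.6.3 with their visits, say whether month 1 is included, and describe collection at virtual follow-ups. Compute the score and count over visits common to both arms, because the delayed arm has one extra. State whether clean samples or days of use is the primary count.
   - If they are not done, make Table 2's self-report measures (any use, days of use) the methamphetamine outcomes. Delete the urine definitions, the score and the methamphetamine f2 in 9.1, both sections numbered 9.2, and Table 2. Record this as a dated outcome change.
2. In 9.1, correct f2 to 0.03 for sexual risk, and for methamphetamine if a continuous measure is kept. Remove or justify f2 on Table 2 rows whose continuous form is N/A, including the continuum row.
3. In 9.1, state that the Aim 1a app-versus-no-app contrast is the arm difference at month 1, for example the month-1 arm-by-time term of the planned mixed model. Report months 3 to 9 as immediate versus delayed access.

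The cost is text, with no new participants. The downside is that, without month-1 urine tests, the randomised app-versus-no-app methamphetamine result is openly self-reported. If no urine tests are done at all, the plan also gives up its only objective and only continuous methamphetamine measure.
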